The activities included were based on a phonological therapy approach. The selection of words used in therapy was based on: Syllabic structure (CV, CVC or CCV) (Brooks & Kempe, 2014); number of syllables (one or two) (Flipsen, 2006); being age appropriate (Fenson et al., 1993); being easily illustrated; and being different from words used for assessment (Lousada et al., 2013; Mendes, Afonso, Lousada, & Andrade, 2013). Words used in therapy were those with which children had difficulty, a criteria used in previous research (Gillon, 2008), and included initial, medial and final word (where applicable) position of the target sound. A list of minimal pair words were selected for *Hearing and Discriminating* and *Phoneme Manipulation*. For the *Rhyme* activity, a list of monosyllabic rhyming words were identified. The criteria used to select these words were: They are all phonologically simple and high frequency, well known by most Portuguese children; two syllable (*Hearing and Discriminating* and *Phoneme Manipulation*) or one syllable (*Rhyme*) words that would rhyme and could be represented by an illustration. Nineteen short stories (one for each phonological process) that used at least twenty words with the target sound were also created, as used by Bowen (2015).

Each target word was illustrated by a professional designer resulting in more than 350 illustrations. A set of three background images was also created (by the same designer) for each short story.

Testing

Assessments of the children with SSD took place at three time points:

- T1 – Baseline and pre-randomisation;
- T2 – Pre-intervention and after a waiting period of 3 months;
- T3 – Post-intervention.

The baseline assessments (T1), pre and post-intervention assessments (T2 and T3), were carried out by the same SLP blind to the study's aims, children allocation and intervention.

In all the assessments (T1, T2 and T3), children's productions were recorded to allow a careful offline analysis (Lancaster, Keusch, Levin, Pring, & Martin, 2010). The recordings were made with a Behringer ECM8000 electret microphone, held by a table support at approximately 1 meter and aligned with the mouth of the children. The microphone was connected to an Olympus LS-100 multi-track linear PCM recorder. The data was recorded in mono format .wav (Windows PCM) without compression at a sample rate of 48000 Hz, with 16 bits per sample. The assessments were made in one of two places: University of Aveiro's Speech, Language and Hearing Laboratory (SLHlab) clinic or the child's school in a quiet room.

To ensure the accuracy of the annotation of the children's phonological abilities, their productions were transcribed phonetically based on perceptual and acoustic analysis using Praat Version 6.0.17. These transcriptions were annotated on two levels: The child's actual production, transcribed phonetically using the SAMPA (Wells, 1997) machine-readable phonetic alphabet; and the child's syllabic structure, using the code C for consonants, V for vowels and G for glides.

The Speech and Language Therapy assessments used were: University of Aveiro's Case History Form for Child Language (Jesus & Lousada, 2010); TFF-ALPE phonetic-phonological test (Mendes et al., 2013); TL-ALPE language test (Mendes et al., 2014); PAOF oro-motor abilities test (Guimarães, 1995); an adaptation to Portuguese of the Speech Participation and Activity of Children - SPAA-C children's questions (McLeod, 2003). Images from the Test of Childhood Stuttering (TOCS) (Gillam, Loga, &

Pearson, 2009) were used to engage the children in conversation and generate spontaneous speech (Limbrick, McCormack, & McLeod, 2013).

Children's transcribed productions were entered into the Automatic Phonological Analysis Tools (APAT) (Saraiva, Lousada, Hall, & Jesus, 2017) by a SLP blind to the study's aims and group allocation using SAMPA (Wells, 1997). The APAT is a valid and reliable tool (Saraiva et al., 2017) to analyse phonological parameters in an automatic way.

The baseline period occurred between the first assessment at baseline (T1) and the pre-intervention assessment (T2). This period was used to organise all the logistics, schedules and places to deliver therapy (clinic and schools). It was also used to assess the children's non-verbal IQ and hearing. The children did not receive any intervention in this time period. All the children waited three months (the same duration as the intervention) before treatment and therefore acted as their own control (Sadlier, Stephens, & Kennedy, 2008). This period allowed us to see the impact of natural maturation on the children's speech and to compare it to performance after intervention.

The mean PCC scores (Shriberg & McLeod, 1982) were used to compare performance of the two groups. The PCC index is one of the most commonly used indexes to quantify the severity of speech impairment in children with SSD during both evaluation and intervention (Wren, McLeod, White, Miller, & Roulstone, 2013). This quantitative measure is highly sensitive to differences in phonological deficits because it provides information pertaining to the two main error types: Omissions and substitutions (Shriberg, Austin, Lewis, McSweeney, et al., 1997; Shriberg, Austin, Lewis, & McSweeney, 1997).

Although there is evidence that only a small number of children have difficulties producing vowels, Watts (2004) recommends doing a more detailed analysis at this

level using the percentage of vowels correct (PVC) in addition to percentage of phonemes correct (PPC).

Generalisation

After each block of intervention, non-intervention words, which included the process targeted in intervention, were given as generalisation words, in order to assess generalisation to non-targeted words (Palle, Berntsson, Miniscalco, & Persson, 2012). The words were selected based on the phonological process trained. They were different from those used during intervention but targeted the same phonological processes and were a close match in terms of production difficulty, frequency in the Portuguese language and syllable structure.

Each child had five opportunities to produce the correct target. These words were used to determine if the child generalised the targeted speech skill and provide important insight into the impact of intervention on a child's phonological system (Baker & McLeod, 2004).

Reliability

The production of all isolated words of two randomly selected children from the three assessment periods (baseline, pre- and post-treatment) were annotated and transcribed by a trained SLP not involved in the study and blind to its aims. Point-to-point reliability was 95.52% (baseline assessment – T1), 94.74% (pre-treatment assessment – T2) and 96.46% (post-treatment assessment – T3). These values are comparable with those reported in other studies in disordered child phonology (Shriberg, Tomblin, & McSweeny, 1999; Shriberg & Lof, 1991) and were considered adequate for the objective of this study. Two children (for each assessment point) represents 9% of speech samples and this percentage is equivalent to what is reported when checking

reliability in other effectiveness studies (Crosbie et al., 2005; Dodd & Bradford, 2000; Lousada et al., 2014; Lousada, Jesus, Capelas, et al., 2013).

Data analysis / statistics

Non-parametric Wilcoxon and Mann-Whitney tests were used to compare data between groups and time periods and multi-comparisons corrections for type-one errors have been made using Bonferroni's correction for every pair of comparisons involving both tabletop and tablet groups. Effect sizes were calculated using Cohen's d with the bias correction given by Hedges's g for the independent samples case (Lakens, 2013). For the purpose of interpreting the effect sizes, the following commonly used benchmarks were used (Field, 2017): Small ($d=0.2$), medium ($d= 0.5$), and large ($d=0.8$). The statistical analysis was made using IBM SPSS Statistics version 22. The level of significance used was 0.05.

References

- Allen, M. M. (2013). Intervention Efficacy and Intensity for Children With Speech Sound Disorder. *Journal of Speech Language and Hearing Research*, 56(3), 865. [https://doi.org/10.1044/1092-4388\(2012/11-0076\)](https://doi.org/10.1044/1092-4388(2012/11-0076))
- Baker, E., & McLeod, S. (2004). Evidence-based management of phonological impairment in children. *Child Language Teaching and Therapy*, 20(3), 261–285.
- Bowen, C. (2015). *Children's Speech Sound Disorders* (2nd ed.). Oxford: Wiley-Blackwell.
- Brooks, P., & Kempe, V. (2014). *Encyclopedia of Language development*. New York: SAGE.

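### The plan names no contrast for its own-control comparison; any statement that therapy exceeded maturation should rest on each child's difference of gains

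*Combined protocol and SAP*

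**What the plan says.** Both arms receive therapy, so the wait from T1 to T2 is the only untreated reference in the trial. The Testing section says of it: "The children did not receive any intervention in this time period". It goes on: "All the children waited three months (the same duration as the intervention) before treatment and therefore acted as their own control". It then gives the wait an analytic purpose: "This period allowed us to see the impact of natural maturation" on the children's speech "and to compare it to performance after intervention".

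The Data analysis / statistics section is one short paragraph. On tests it says: "Non-parametric Wilcoxon and Mann-Whitney tests were used to compare data between groups and time periods". Bonferroni is applied as a "correction for every pair of comparisons involving both tabletop and tablet groups". A bias-corrected effect size is described for independent samples. No section defines a gain, a difference of gains, or the result that would support a statement about therapy against maturation.

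**The concern.** Children in this age range improve without treatment, and that is why the design includes a wait as long as the therapy. The wait serves as a control only if the change during it is compared formally with the change during therapy. The analysis wording allows that comparison. It equally allows separate tests of T1 against T2 and of T2 against T3.

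The separate tests are valid for what they test, which is change between two assessments. They do not separate therapy from maturation. The T2–T3 change contains both, and two tests with different significance verdicts are not a test that the two changes differ. A report that therapy did better than natural maturation would therefore be supported under one reading of the section and unsupported under the other.

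**Working it through.** **1. What the wording settles.** The Testing section uses the term for a period of time for the T1–T2 interval, which favours a comparison of intervals. The same section introduces T1, T2 and T3 as points in time, which points the same way. The Reliability section, just before the analysis paragraph, speaks of recordings "from the three assessment periods (baseline, pre- and post-treatment"), where the periods are the assessments themselves. The usage conflicts, so neither reading can be fixed from the text.

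**2. What each test estimates.** Let m1 and m2 be the untreated mean gains in the two periods, and θ the extra gain from therapy.

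- Mean of T2−T1 = m1
- Mean of T3−T2 = m2 + θ
- Mean of D = (T3−T2)−(T2−T1) = T3 − 2·T2 + T1 is θ + (m2 − m1)

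A T2–T3 test responds to m2 even when θ = 0. D isolates θ, provided m1 = m2.

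**3. Inputs.** From the documents: 22 children (Participants), significance level 0.05 (Data analysis / statistics), and three assessments (Testing). Assumed: two-sided tests, normal data, error SD of 1 at each assessment, equal maturation in both periods, θ = 0. The plan states no SD, maturation rate, power or sample-size calculation, so it has no figure to reproduce.

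**4. Spread under three models.**

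| Model for between-child variation in gain | SD of T3−T2 | SD of D |
|---|---|---|
| None | √(1+1) = 1.41 | √(1+4+1) = 2.45 |
| SD 1, independent in each period | √(1+1+1) = 1.73 | √(6+2) = 2.83 |
| SD 1, shared by both periods | √(1+1+1) = 1.73 | √6 = 2.45 (shared part cancels) |

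**5. Results with no therapy effect.** There were 40,000 simulated trials per setting with exact signed-rank critical values. Ranges cover the three models, and a fresh rerun agreed within about one percentage point.

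| Maturation per period (error SD) | T2–T3 improved significantly | T2–T3 improved significantly, T1–T2 not significant |
|---|---|---|
| 0 | 2.3–2.4% | 1.9–2.2% |
| 0.25 | 8.4–11.1% | 7.8–10.8% |
| 0.5 | 23.2–32.5% | 17.6–26.9% |
| 0.75 | 46.2–62.9% | 24.7–29.8% |
| 1 | 70.2–86.3% | 13.5–24.2% |
| 1.5 | 96.3–99.6% | 0.4–3.7% |

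The middle column is not an error rate, because the children do improve under this model. It misleads only if it is read as a therapy effect. The last column is the relevant one. At 0.25–1 error SD, the gain contrast does not significantly favour therapy in about 80–92% of the trials showing the two-test pattern.

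The test of D favours therapy in 2.31% of trials (exact; 4.62% counting both directions), whatever the maturation rate, as long as it is equal in the two periods.

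**6. Power of the gain contrast.**

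| Extra gain θ (error SD) | Pooled, n = 22, α = 0.05 | By arm, 11 per arm, α = 0.025 (both assumed) |
|---|---|---|
| 0.5 | 11–14% | 4–5% |
| 1 | 33–42% | 11–15% |
| 2 | 86–94% | 41–53% |

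Because the mean of D is θ + (m2 − m1), an untreated gain larger in the second period by 0.5 or 1 error SD would falsely favour therapy at the same pooled rates, 11–14% and 33–42%.

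**The case against.** The strongest reply is that the gain comparison may be exactly what was meant. The Testing section applies the period term to the wait, calls the assessments points in time, and says that the wait is compared with performance after intervention. That reading is at least as natural as tests of scores, and this stands: the defect is an unsettled specification, not a demonstrated wrong analysis.

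A reader might infer that the trial ran separate tests and claimed efficacy from T2–T3 alone, or from one significant and one non-significant result. The documents do not support this. No section makes such a claim or shows that route. A reader might also infer from the independent-samples wording that no paired effect size was calculated. It says only where the bias correction applies.

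Three further objections stand. The two-test pattern is common only in a middle band of assumed maturation, and nothing in the documents places this trial there. The Testing section ties the percentage of consonants correct (PCC) to the comparison of the two groups, so the own-control outcome is itself unstated. The proposed contrast is also modest evidence, with low power and an untestable assumption of equal untreated gains.

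None of this removes the gap. The plan announces a comparison, and its analysis text admits one test that answers it and others that do not.

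**Conclusion.** The point holds as a cheap improvement of minor severity. The documents announce an own-control comparison and leave its contrast unnamed, and only a gain-against-gain test answers that question. Under the assumed values, relying on the two-test pattern would suggest a therapy advantage that does not exist in about 2% of trials with no maturation, 8–30% at 0.25–1 error SD and 0.4–4% at 1.5, against 2.3% for the gain contrast. These figures assume no therapy effect and equal maturation in both periods. They do not estimate the size of the problem in this trial.

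The comparison is non-randomised, and no section makes it the main question. It would be wrong to carry the concern over to tabletop versus tablet: both arms mature and both wait, so the randomised comparison is unaffected.

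**What to change.** In Data analysis / statistics:

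- Base any statement that therapy exceeded maturation on each child's (T3−T2)−(T2−T1), tested by Wilcoxon signed-rank, with an estimate and 95% CI.
- Name the outcome. PCC is the obvious choice, but the plan must say so.
- State whether the 22 children are pooled or each arm is tested separately with Bonferroni. Pooling gives more power but averages over the two delivery modes.
- Report T1–T2 and T2–T3 changes descriptively, and make no efficacy claim from T2–T3 alone.
- Label the contrast post hoc if it is added after T3 data were seen. The Reliability section already reports T3 agreement ("and 96.46% (post-treatment assessment"), so this may well apply.

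The cost is a few sentences and one derived variable from assessments already made. The result will look less favourable than a raw T2–T3 test, power is modest, and a post hoc contrast carries less weight. Bias remains from fixed order, practice and non-linear maturation. Regression to the mean after selection at T1 would tend to inflate the waiting gain and so bias the contrast against therapy. The report should state these limits beside the estimate.

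### The tabletop-tablet comparison makes no named adjustment for the pre-therapy T2 score; adding one baseline-adjusted analysis would usually gain precision, by an amount the documents do not fix

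*Combined protocol and SAP*

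**What the plan says.** The Data analysis / statistics section is the whole analysis plan. It states that Wilcoxon and "Mann-Whitney tests were used to compare data between groups and time periods". I read Wilcoxon as the paired test over time and Mann-Whitney as the test between arms. The effect size is Cohen's d with the Hedges correction "for the independent samples case". Multiplicity is handled by a Bonferroni "correction for every pair of comparisons involving both tabletop and tablet groups", which adjusts p-values and not baseline. No covariate, regression model or confidence interval is named.

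The Testing section says that mean PCC scores "were used to compare performance of the two groups", without saying whether the T3 score or the T3-T2 change is compared. It also shows that T2 is a pre-therapy measurement. Speech is recorded at T1, T2 and T3, and of the wait between T1 and T2 it says "The children did not receive any intervention in this time period".

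**The concern.** Tabletop against tablet is the only comparison protected by randomisation. The maturation comparison is within child and cannot separate the two delivery modes. With 22 children precision is scarce, and a T2 score that predicts T3 explains variation that an unadjusted comparison of T3 leaves as noise. Using it needs no new data.

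Two related gaps make this worse. The tested variable is not stated, so a reader cannot tell whether T2 was partly used through change scores or not used at all. And with no interval planned, a non-significant p-value does not show which differences between delivery modes remain plausible.

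**Working it through.** **Inputs from the document.** 22 children (Participants); random allocation to two groups, arm sizes not given (Intervention); significance level 0.05, sidedness not given (Data analysis / statistics). No power calculation, SD, T2-T3 correlation or target difference is stated, so the plan has no figure to reproduce.

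**Assumed.** 11 per arm, two-sided 0.05 before Bonferroni, near-normal PCC with equal SD at T2 and T3, true difference 0.8 SD, and a range of T2-T3 correlations r. The plan gives 0.8 only as a benchmark for reading effect sizes, not as a design target.

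**Step 1: variance of the between-arm difference, in SD squared.**
- T3 alone: 2/11.
- T3-T2 change: (2/11) × 2(1 − r).
- ANCOVA on T2: (2/11) × (1 − r²) × (1 + 1/18). The last factor, 19/18, is the cost of estimating the slope.

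| r | ANCOVA / T3 | ANCOVA / change |
|---|---|---|
| 0.3 | 0.91 × 19/18 = 0.96 | 0.96/1.4 = 0.69 |
| 0.5 | 0.75 × 19/18 = 0.79 | 0.79/1.0 = 0.79 |
| 0.7 | 0.51 × 19/18 = 0.54 | 0.54/0.6 = 0.90 |
| 0.8 | 0.36 × 19/18 = 0.38 | 0.38/0.4 = 0.95 |
| 0.9 | 0.19 × 19/18 = 0.20 | 0.20/0.2 = 1.00 |

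ANCOVA equals T3 when r² = 1/19, so r is about 0.23. It equals change when 1 + r = 36/19, so r = 17/19, about 0.89. It is the more precise of each pair above the first value and below the second.

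**Step 2: power and interval width** (simulation, 40,000 trials per setting, exact Mann-Whitney).

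| r | 0.3 | 0.5 | 0.7 | 0.8 | 0.9 |
|---|---|---|---|---|---|
| Mann-Whitney on T3, power % | 40 | 40 | 40 | 40 | 40 |
| Mann-Whitney on change, power % | 30 | 40 | 60 | 77 | 97 |
| ANCOVA on T2, power % | 44 | 52 | 68 | 82 | 98 |
| 95% CI half-width, T3 (SD) | 0.88 | 0.88 | 0.88 | 0.88 | 0.88 |
| 95% CI half-width, change (SD) | 1.04 | 0.88 | 0.68 | 0.56 | 0.39 |
| 95% CI half-width, ANCOVA (SD) | 0.86 | 0.78 | 0.65 | 0.54 | 0.39 |

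Type I error was 4.3% to 5.3% for every method. An unadjusted t-test on T3 has 43% power, so about 3 points of the gain over Mann-Whitney on T3 come from the parametric test and the rest from the covariate.

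**Step 3: sensitivity at r = 0.7** (Mann-Whitney on T3 / Mann-Whitney on change / ANCOVA).
- True difference 0.5 SD: 19/28/33%.
- Arms of 14 and 8: 36/54/64%.
- Significance level 0.05/3 = 0.0167, assuming three outcomes: 24/41/49%.

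**Step 4: bounded scores** (logit-normal, 0.8 SD and r on the latent scale).
- Mid-range (assumed T2 mean 64%, SD 13, gain 16 points), r = 0.7: 40/28/64%, same order as Step 3.
- Near ceiling (assumed T2 mean 81%, SD 11, gain 12 points), r = 0.3/0.5/0.7/0.8/0.9: linear ANCOVA 37/43/57/70/90%, rank-based (Quade) ANCOVA 43/49/62/75/92%, Mann-Whitney on T3 40%, Mann-Whitney on change 10/10/12/12/12%.

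Near the ceiling with r = 0.3, linear ANCOVA therefore loses about 3 points to Mann-Whitney on T3, and at r = 0.5 it gains about 3. The rank-based version does not fall below Mann-Whitney on T3 in either case. With normal data it does fall below Mann-Whitney on change from r = 0.8, so it is not a sensible default for every outcome.

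**The case against.** **The test is valid, and a rank test is defensible for a bounded percentage in 22 children.** This stands. A reader might infer that leaving out T2 biases the comparison. It does not: chance imbalance at T2 adds noise to an unadjusted randomised comparison, and the Mann-Whitney test keeps its error rate.

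**The gain is not established by the documents.** This also stands. A reader might take the step from 40% to 68% or 82% as the plan's actual loss. That holds only if raw T3 was tested, which the documents never state, and only at the assumed correlation, difference and arm sizes. If change was tested, the near-normal gain at r = 0.5/0.7/0.8 is 52 − 40 = 12, 68 − 60 = 8 and 82 − 77 = 5 points. In the bounded settings of Step 4, however, change does much worse than ANCOVA, so the gain is modest only for near-normal scores.

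**The analysis may already be done.** The section is in the past tense ("corrections for type-one errors have been made"), and the Reliability section reports T3 transcription agreement of 96.46%, so at least some T3 data had been processed. A reader might conclude that ANCOVA should replace the Mann-Whitney test. Replacing the stated test once outcomes may be known is poor practice. So is choosing between linear, permutation and rank methods after seeing the data.

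**T2 follows allocation.** It does (Intervention). But no therapy preceded it, tablets were handed out only when therapy began, and the assessor was blind to allocation. The documents do not say when families learned the allocation, but nothing in them suggests that T2 was affected. T1 is strictly pre-randomisation but may predict less well, since the wait was meant to capture change ("This period allowed us to see the impact of natural maturation"). If the T1-T3 correlation is r², power with T1 alone at r = 0.5/0.7/0.8 is 43/51/62%, against 52/68/82% with T2.

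**Conclusion.** The point holds as an efficiency improvement, not an error. No baseline adjustment is named for the single randomised contrast, and a usable pre-therapy score exists. Under the near-normal assumptions above, the gain in power at r = 0.5/0.7/0.8 is about 12/28/42 points if T3 was tested and 12/8/5 points if change was tested. It disappears against T3 below r of about 0.23 and against change above about 0.89, and it can be a small loss against T3 near the ceiling with a low correlation. The correlation, SD, arm sizes, sidedness and number of Bonferroni comparisons are all unstated, so confidence in the size is only medium.

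Adjustment would not make 22 children enough to exclude moderate differences. The difference detectable with 80% power falls from about 1.26 SD (unadjusted t-test) to about 0.92 SD at r = 0.7. The documents support neither a claim of bias nor a claim that any particular amount of power was lost.

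**What to change.** 1. State whether the Mann-Whitney test uses T3 or T3-T2 change, whichever was in fact used, and keep it as the stated analysis.
2. Add one baseline-adjusted analysis of the between-arm difference. Label it post hoc if outcomes are known; make it the main analysis only if they are not.
3. Fix one method per outcome now, with no switching on the data:
   - PCC and PPC: ANCOVA of T3 on arm and T2, reporting the adjusted mean difference with its 95% CI.
   - PVC: rank-based (Quade) ANCOVA on T2. Testing notes that "there is evidence that only a small number of children have difficulties producing vowels", so scores near the ceiling are plausible. Quade's method gives no interval in percentage points; a Hodges-Lehmann shift with its interval can accompany the Mann-Whitney test.
4. Apply the stated Bonferroni correction to the added analyses and say how many comparisons it covers.

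Cost: no new data, one extra model per outcome, one degree of freedom, and a linearity assumption for a bounded percentage. Item 1 and an interval (Hodges-Lehmann, or one for g) need no ANCOVA and are worth doing in any case.

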Table to Tablet (T2T): A Novel Intervention Framework for Children With Speech Sound Disorders

1st of January 2017

University of Aveiro
Aveiro, Portugal

This study is a randomised control trial. The first step was the creation of partnerships between the University of Aveiro and schools in the Aveiro region (Jesus, Martinez, Valente, & Costa, 2017). Teachers were asked to identify children that they thought had immature or poor speech. All identified children were then assessed (T1). Due to the fact that the project was only selecting children with SSD, most other children (with different diagnoses) were referred to external (to the project) SLPs. The children who fitted the inclusion criteria were then randomly allocated to one of two groups (tabletop or tablet) and were assessed again after a waiting period of 3 months (T2). After this second assessment, the children had intervention and were assessed at post-intervention (T3).

Participants

Twenty-two Portuguese children (four girls and eighteen boys) with phonologically-based SSD, with a mean age of 57 months were selected. This disproportionate number of males-females is a typical distribution (70-80% boys) in the Portuguese population, and has been reported in previous studies (Jesus, Lousada, Domingues, Hall, & Tomé, 2015). Children were assessed and diagnosed as having phonologically-based SSD after an extensive assessment by a Speech and Language Pathologist (SLP), an audiologist and a psychologist.

Participant inclusion criteria were:

- Age range from 3;6 to 6;6;
- European Portuguese as first and only language;
- No impairments on oro-motor structure and function (assessed with the Protocolo de Avaliação Oro Facial – PAOF (Guimarães, 1995);
- No symptoms of verbal dyspraxia;
- Age appropriate receptive language (assessed with the Teste de Linguagem ALPE – TL-ALPE (Mendes, Afonso, Lousada, & Andrade, 2014));
- Audition of 20 dB or lower in the frequencies 500, 1000, 2000 and 4000 Hz;
- Age appropriate non-verbal IQ assessed with the Wechsler Preschool and Primary Scale of Intelligence-Revised – WPPSI-R (Wechsler, 2003);
- Presenting at least two phonological processes at pre-intervention time (Crosbie, Holm, & Dodd, 2005; Dodd, Zhu, Crosbie, Holm, & Ozanne, 2002).

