Parents/caregivers were invited to be present in therapy sessions either at their child's school or at the clinic, and short homework tasks were given at the end of each session to complete for the following session.

In the tabletop group the homework activities were work sheets focusing on the targeted phonological processes, and in the tablet group, homework was based on four different computerised games.

Each child allocated to the tablet group received a tablet with the games installed at the beginning of the intervention. In each session an information sheet about the game that should be played that week was given to the caregiver.

Furthermore, generalisation tasks for each phonological process were created. These tasks are included to allow SLPs to test if changes in a child's phonological system go beyond the treatment words and targets (Bowen, 2015).

The allocation to one of the interventions (with same content but different delivery method – tabletop or tablet) took place during the waiting period, after the selection process and before the pre-intervention assessment. Each child was given a number from 1 to 22 and randomly allocated to one of the two groups. The numbers were randomised using an online tool (True random integer sequence generator based on atmospheric noise data <https://www.random.org/sequences/>; RANDOM.ORG; Randomness and Integrity Services Ltd).

The phonologically based intervention consisted of a combination of phonological awareness activities (Lousada et al., 2013) adapted from Gillon and McNeill's (2007) phonological awareness programme, Hodson and Paden's (1991) auditory bombardment, and discrimination and listening tasks from Lancaster (2008).

The criteria taken into account to choose the target phonological processes were: Frequency – occurring at least at a 40% rate in the child's speech (Hodson & Paden, 1991); intelligibility (Dodd & Bradford, 2000; Lousada et al., 2014) – less than 2/3 (66%) of the utterances of a child can be understood by unfamiliar listeners (Gordon-Brannan & Hodson, 2000, p. 146); stimulability – including stimuable sounds (Dodd & Bradford, 2000); developmental – earlier acquiring sounds (Dodd & Bradford, 2000; Mendes et al., 2013).

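### Bonferroni's correction is valid, but Holm's step-down gives the same family-wise guarantee and never rejects less, so it is a cheap optional improvement of modest, assumption-dependent size

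*Combined protocol and SAP*

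**What the plan says.** The Data analysis / statistics section gives the tests: "Non-parametric Wilcoxon and Mann-Whitney tests were used to compare data between groups and time periods". It then says that "multi-comparisons corrections for type-one errors have been made using" Bonferroni's "correction for every pair of comparisons involving both tabletop and tablet groups", and that "The level of significance used was 0.05". Hedges-corrected standardised differences are planned as effect sizes. No step-down or other sequential procedure is mentioned, and no simultaneous confidence intervals are planned.

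The section does not say how many comparisons form a family, what the adjusted level is, or which outcomes and time points are included. The Testing section says mean PCC scores "were used to compare performance of the two groups" and also mentions PVC and PPC, without labelling any of them primary.

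On size, the Participants section has "Twenty-two Portuguese children (four girls and eighteen boys) with phonologically-based SSD", and the Intervention section says "Each child was given a number from 1 to 22 and randomly allocated to one of the two groups". The numbers per arm are not stated.

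**The concern.** Bonferroni tests every member of a family of m hypotheses at 0.05/m. Holm tests the smallest p-value at 0.05/m. Only if that is rejected does it test the next at 0.05/(m−1), and so on. Both keep the family-wise error at or below 0.05 whatever the dependence between tests, and Holm can only add rejections. A common reason to stay with the single-step version is that it yields simple simultaneous confidence intervals. This plan reports none, so that reason does not apply.

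What is at stake is avoidable loss of power in a 22-child trial. The two arms receive the same content by different delivery modes, and each child's waiting period serves as its own control. Readers will therefore look at whether both arms improved. That is the result on which the two procedures can differ.

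**Working it through.** The plan gives no power, sample-size or adjusted-alpha figure, so there is none to reproduce.

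**Inputs from the document:** level 0.05; Wilcoxon and Mann-Whitney tests; Bonferroni; 22 children in two groups.

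**Assumptions, because the document is silent:** two-sided tests; 11 children per arm; exact signed-rank tests on paired time points; a family of m = 2 (one within-arm test per arm); independent arms; normal differences. Standardised changes of 0.5 and 0.8 are taken from the plan's interpretation benchmarks, and 1.2 is added. None of these is a design effect.

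**Step 1: attainable levels.** With 11 pairs there are 2^11 = 2,048 sign patterns. The largest exact two-sided level not above 0.025 is 50/2,048 = 0.0244. The largest not above 0.05 is 86/2,048 = 0.0420.

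**Step 2: single-test power.** Let a = P(p ≤ 0.025) and b = P(p ≤ 0.05), by simulation (400,000 samples of 11 per effect size).

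**Step 3: formulas for two equal real effects.**
- Per-test power: Bonferroni a; Holm a + a(b − a).
- Both declared: Bonferroni a²; Holm a² + 2a(b − a).
- At least one declared: 1 − (1 − a)² under either.

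| True change | a | b | Per test, Bonferroni → Holm | Both, Bonferroni → Holm | At least one, either |
|---|---|---|---|---|---|
| 0.5 | 0.207 | 0.285 | 20.7% → 22.3% | 4.3% → 7.5% | 37.1% |
| 0.8 | 0.512 | 0.619 | 51.2% → 56.7% | 26.2% → 37.2% | 76.2% |
| 1.2 | 0.872 | 0.926 | 87.2% → 91.9% | 76.0% → 85.5% | 98.4% |

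For example, at 0.8: 0.512 + 0.512 × (0.619 − 0.512) = 0.567, and 0.512² + 2 × 0.512 × 0.107 = 0.372. Results significant in one arm only go from 2a(1 − a) = 2 × 0.512 × 0.488 = 50% to 2a(1 − b) = 2 × 0.512 × 0.381 = 39%.

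**Step 4: only one effect real.** The real test gains 0.0244 × (b − a). That is 0.0244 × 0.107 = 0.0026 at 0.8, or 0.3 percentage points. The null member's rejection rate goes from 0.0244 to 0.0244 + (0.0420 − 0.0244) × a. At 0.8 this is 0.0244 + 0.0176 × 0.512 = 3.3%; at 1.2 it is 0.0244 + 0.0176 × 0.872 = 4.0%. With both null, family-wise error is 1 − (1 − 0.0244)² = 4.8% under either method.

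**Step 5: other families** (simulation, 100,000 replicates, 11 per arm).
- Three Mann-Whitney tests (PCC, PVC, PPC; correlation 0.6 assumed): per-test power 9% → 10.5% at d = 0.5, and 24% → 28% at d = 0.8.
- Two Wilcoxon tests and one Mann-Whitney test (within-arm change 1.2 in one arm and 1.2 + 0.8 = 2.0 in the other, between-arm d = 0.8): Mann-Whitney power 24% → 38%, the largest single-test gain found.
- Six Wilcoxon tests, four with real effects: 28% → 32% at 0.8, and 67% → 76% at 1.2.
- One Mann-Whitney test with no correction at all: power 7% (d = 0.2), 19% (0.5) and 40% (0.8).

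**The case against.** The strongest reply is that this is a preference. Bonferroni is a recognised, conservative method, and nothing in the section is wrong or contradictory. That stands: the point is an improvement and does not correct an error. It does not defeat the point, because a procedure with the same guarantee that never rejects less needs no trade-off to justify it.

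A second reply is that the family is undefined, so Holm could not be applied reproducibly either. This is true, and it is the larger gap in that sentence. But Holm needs exactly the family that Bonferroni needs and no pre-set ordering, so the gap bears equally on both.

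Third, the both-arms figure is the favourable metric. Per-test gains are smaller, and inferring an arm difference because only one arm reached significance is unsound under either procedure. Holm still leaves 39% of such results at 0.8. This also stands.

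Fourth, Holm is not wholly free. It stays within 5% but uses more of the allowance, as the null-member figures show.

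A reader might also infer that every corrected test rests on about 11 children. The document does not support that: arm sizes are unstated, and a between-group Mann-Whitney test uses both arms. Nor may one infer that the gain grows with the number of tests. At 0.8 the per-test gain is about 5 to 6 points for two tests, both real, and about 4 for six tests of which four are real. It depends on how many effects are real and how large they are.

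**Conclusion.** The point holds as an optional, low-cost improvement. Holm dominates Bonferroni at the same family-wise level, and the plan shows no reason to prefer the single-step version. Under the assumed family of two with equal real effects and 11 per arm, the per-test gain is about 2 percentage points at a change of 0.5 and about 5 at 0.8 and 1.2. The chance of declaring both arms at 0.8 rises by 11 points. Gains can be larger when other effects in the family are large, and are close to nil when only one effect is real.

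It would be tempting to conclude that the planned analysis is invalid, or that Holm would rescue an underpowered trial. Neither follows. Bonferroni controls the error rate as claimed. Holm leaves the chance of at least one finding unchanged, and uncorrected Mann-Whitney power is only 40% at d = 0.8 with 11 per arm. All these sizes are scenarios, because family size, arm sizes and expected effects are not in the document.

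**What to change.** In Data analysis / statistics, name the Holm-Bonferroni step-down in place of Bonferroni's correction for the same families, and report Holm-adjusted p-values. With ordered p-values p(1) ≤ … ≤ p(m), the adjusted value for p(j) is the largest of min(1, (m − i + 1) × p(i)) over i ≤ j. This can be done by hand from the raw p-values, so the choice of SPSS is no obstacle. The number and membership of each family should be written down at the same time, since either method needs it.

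Timing matters. The section is written in the past tense, and the Reliability section already reports post-treatment transcription agreement. If results are known, keep Bonferroni as the planned analysis and show Holm-adjusted p-values beside it, labelled post hoc. A silent switch to the less strict rule would not break the 5% bound, but it would be an undeclared change of plan.

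The cost is one phrase and a few multiplications, plus the somewhat fuller use of the 5% allowance shown above. No extra data are needed.
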